## 8.3 Statistical analysis:

Matched student t-test will be used for continuous variables and the Chi-square test will be used for categorical variables. The UCSF Department of Epidemiology and Biostatistics will be involved in the formal statistical analysis.

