## 7.0 Study Design

**7.1 \* Study design (Help Text updated 9/13):**

Glucagon transiently decreases peristalsis of smooth muscle in the gastrointestinal tract. It is widely used by radiologists to improve diagnostic yields of upper and lower GI barium contrast examinations. Glucagon is also routinely administered intravenously for all endoscopic retrograde cholangiopancreatography (ERCP) throughout the United States to facilitate cannulation of the duodenal papilla and sphincterotomy. Glucagon has been used at the dose of 1-3 mg intravenously by [name] in over 5000 ERCP examinations. However, the role of glucagon in facilitating colonoscopy remains unanswered and is not considered "routine". Several studies have evaluated the effect of glucagon on colonoscopy with varying results. No large scale randomized controlled trial has been performed to conclusively establish the effect of routine glucagon administration prior to colonoscopy. The investigators plan to carry out a randomized, double blind, placebo controlled trial that studies key parameters of a colonoscopy such as cecal intubation time, withdrawal time, total procedure time, adenoma detection rate, endoscopist's assessment of the difficulty of the procedure, patient comfort, and patient's willingness to undergo a repeat colonoscopy.

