Colonoscopy is commonly complicated by colonic spasms, particularly in individuals consuming a low residue diet, this leading to patient discomfort, longer procedure times, increased use of sedatives and operator fatigue. Glucagon, an antispasmodic agent, has been demonstrated to reduce intraluminal colonic pressure, colonic wave activity and colonic motility index and is routinely administered prior to colonoscopy by some gastroenterologists. As mentioned above, intravenous glucagon is routinely used during every ERCP examination throughout the United States of America. However, its effect on duration of colonoscopy, adenoma detection rate, patient comfort and operator fatigue has not been definitively answered. There are four previous studies that have evaluated the use of glucagon during colonoscopy and produced conflicting result. Three of these studies were performed prior to 1995 and cannot account for technological improvement leading to improved colonoscope performance. For instance, the first study performed in 1978 took an average of 50 minutes to perform a colonoscopy, almost twice as long as a colonoscopy performed today. Furthermore, each study was limited by small sample sizes (~30 subjects in each study group) and produced conflicting results. One of the studies demonstrated that glucagon decreases total colonoscopy time while the other two studies demonstrated no effect. A recent randomized control trial demonstrated improved cecum insertion time, lower patient pain score and easier scope manipulation with glucagon supplementation but failed to produce a significant clinical impact due to a small sample size (30 subjects in each study group).

We propose to definitively demonstrate the positive effect of glucagon during colonoscopy by performing a placebo-controlled randomized clinical trial involving a large sample size. We aim to evaluate cecum intubation time, total procedure time, adenoma detection rate, degree of spasm, adequacy of visualization, and patient pain score. We will also determine blood glucose level at the end of the procedure to determine the effect of glucagon therapy during colonoscopy. The primary endoscopist for this study, [name], performs or supervises ~15 colonoscopies per week therefore we can expect to enroll at least 300 outpatient subjects over a one-year period.

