### 10.4 Explain how and why the number of subjects was chosen (Help Text updated 9/13):

We base our sample size calculation on the results of the recent randomized control trial comparing glucagon versus placebo prior to colonoscopy. In the study, the mean cecum intubation time was 294 seconds in the glucagon group and 370 seconds in the placebo group with a standard deviation of 140 seconds. Using a power of 0.9 and an  $\alpha$  of 0.05, a sample size of 67 participants in each study arm will be needed for this study.

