## 14.0 Procedures

**14.1 \* Procedures/Methods (Help Text updated 9/13) For clinical research list all study procedures, test and treatments required for this study, including when and how often they will be performed. If there are no clinical procedures, describe the Methods:**

1. We will create 400 cards with either glucagon or placebo written on them in a 1:1 distribution. These cards will be shuffled and placed individually into non-descript envelopes. The envelopes will be handed to our research assistant and shuffled again and each envelope will be placed in a larger envelope serially labeled from 1-400.

2. Medical records of patients presenting for a colonoscopy at the SFGH outpatient endoscopy clinic (3D) will be reviewed for inclusion into our study. On the day of the procedure, study coordinators fluent in the patient's primary language will approach the patients prior to any procedural activity. They will be informed about the medication, the proposed study and potential medication side-effects and asked of their willingness to participate in the research study. Any questions the patients may have will be answered by the study coordinators in the patient's primary language. If the patient agrees to be part of the study, he/she will be serially assigned a study number ranging from 1-400. If the patient refuses to participate in the study, they will undergo routine colonoscopy (they may still receive glucagon outside the study since some gastroenterologists routinely prescribes glucagon prior to all colonoscopies).

3. While alone in the Med-Room, nurses will open the envelope with the patient's study number and draw up 1 mg of glucagon or 1 mL of NS in a covered syringe preventing visualization of syringe content. Glucagon is reconstituted in 1mL of normal saline therefore it will be impossible to identify patient randomization even if the syringe content is visualized.

4. The patient will be given routine intravenous procedural sedation and one minute prior to the start of the colonoscopy, the nurse will be instructed to deliver the study drug.

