**14.2 Interviews, questionnaires, and/or surveys will be administered or focus groups will be conducted:**

Yes  No

List any standard instruments used for this study:

Please refer to attached Patient and Endoscopist questionnaire. Both questionnaires utilize a visual analog scale to gauge patient and endoscopist response. We will use a 100mm visual analog scale and the distance from the left endpoint will be taken as the response value. This technique has been validated and previously used for endoscopic studies. These forms will be translated into both Spanish and Chinese.

Attach any non-standard instruments at the end of the application.

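### Section 8.3 names a matched t-test for continuous outcomes, but the two randomised arms are independent and nothing defines the pairs

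*Combined protocol and SAP*

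**What the plan says.** Section 8.3 (Statistical analysis) of the combined protocol and SAP is the only place that names a test for continuous outcomes: "Matched student t-test will be used for continuous variables and the Chi-square test will be used for categorical variables". It adds that a biostatistics department will take part in the formal analysis. It gives no matching variable and no rule for forming pairs.

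The design is set out elsewhere:

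- Section 7.1: "The investigators plan to carry out a randomized, double blind, placebo controlled trial".
- Section 14.1, step 1, on the 400 allocation cards, half for each treatment: "These cards will be shuffled and placed individually into non-descript envelopes".
- Section 14.1, step 2, on a consenting patient: "he/she will be serially assigned a study number ranging from 1-400". Step 3 has the nurse prepare either glucagon or saline for that patient.
- Section 10.4, after quoting two group means and one SD: "a sample size of 67 participants in each study arm will be needed for this study".

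The continuous outcomes in sections 8.2 and 14.1 are cecal intubation time, withdrawal time, total procedure time and amount of sedative. Section 14.2 adds the patient and endoscopist ratings: "We will use a 100mm visual analog scale and the distance from the left endpoint will be taken as the response value".

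**The concern.** A paired t-test works on within-pair differences. It can be computed only if each observation in one arm has a specified partner in the other, or if each patient supplies both values. This trial has neither. Patients are randomised one at a time to one treatment, and each outcome is recorded once, with no baseline value to pair against.

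An analyst following section 8.3 would have to invent a pairing, for example by enrolment order, by study number or after looking at the data. Each choice gives a different p-value and confidence interval from the same data. If the arms are unequal, the surplus patients in the larger arm have no partner and drop out. The rule covers every continuous outcome, including cecal intubation time, on which the trial is sized (no outcome is named as primary).

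**Working it through.** **Inputs.** Means 294 s and 370 s, SD 140 s, power 0.9, alpha 0.05 and 67 per arm (section 10.4). Enrolment of 200 (sections 10.1 and 10.2), taken as 100 per arm for the precision calculations. A deck of 400 cards, 200 for each treatment (section 14.1). Assumed: two-sided alpha, since the plan does not state sidedness, and normally distributed data.

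**1. The plan's own sample size.** Difference: 370 − 294 = 76 s.

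- Independent groups: n per arm = 2 × [140 × (1.960 + 1.282) / 76]² = 71.3, so 72 (73 with the exact t distribution).
- Matched pairs, reading 140 s as the SD of the differences: [140 × (1.960 + 1.282) / 76]² = 35.7, so 38 pairs with the exact t distribution.

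Neither gives 67. A paired calculation reaches 67 only with a within-pair correlation of about 0.06 to 0.10, which the plan does not state. So section 10.4 does not show that matching was intended. Its inputs (two group means, one SD, a number per arm) are those of an independent-groups comparison. The gap between 67 and 72 is a separate matter, and this point does not depend on it.

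**2. What the pairing does to the interval.** Write SE = 140 × √(2/100) = 19.80 s.

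- Independent groups: half-width = t(0.975; 198 df) × SE = 1.972 × 19.80 = 39.0 s. At 76 s the 95% CI is 37 to 115 s, p = 0.00017.
- Paired: half-width = t(0.975; 99 df) × SE × √(1 − r) = 1.984 × 19.80 × √(1 − r) = 39.3 × √(1 − r) s. Here r is the sample correlation that the chosen pairing happens to produce.

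The observed mean difference is the same for every complete pairing; only r moves. With random pairing r is centred on 0 with SD 1/√99 = 0.10, so its central 95% range is about ±0.197. That gives half-widths of 39.3 × √0.803 = 35.2 s to 39.3 × √1.197 = 43.0 s. A simulation of 5,000 random pairings gave 35.2 to 43.1 s.

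**3. When the verdict changes.** Same simulation, random pairings made without regard to outcome:

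| Observed difference | Independent p | Paired p, central 95% | Pairings that change the 0.05 verdict |
|---|---|---|---|
| 20 s | 0.314 | 0.266 to 0.358 | 0% |
| 30 s | 0.131 | 0.094 to 0.170 | 0% |
| 40 s | 0.045 | 0.027 to 0.067 | 35% |
| 50 s | 0.012 | 0.006 to 0.023 | 0% |
| 60 s | 0.0028 | 0.0011 to 0.0066 | 0% |
| 76 s | 0.00017 | 0.00004 to 0.0007 | 0% |

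On a one-second grid, at least 1% of pairings change the verdict only from 35 to 43 s. The formula in step 2 agrees at 40 s: significance is lost when 39.3 × √(1 − r) exceeds 40, that is when r < −0.037, which has probability of about 0.36.

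**4. Pairings that are not random.** Pairing both arms in sorted order pushes r towards 1. At 20 s it gave p below 10⁻¹³, against 0.31 for independent groups. Pairing in opposite order pushes r towards −1:

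- At 50 s, t = 50 / (19.80 × √2) = 1.79, p about 0.077, against 0.012 for independent groups.
- At 76 s, t = 76 / 28.0 = 2.71, p about 0.008, so the verdict survives.

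**5. Long-run error rates, outcome-blind pairing** (40,000 simulated trials per effect):

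| True difference | Rejects, independent | Rejects, paired | Tests disagree |
|---|---|---|---|
| 0 s | 5.07% | 5.07% | 0.9% |
| 40 s | 52.0% | 51.6% | 3.1% |
| 76 s | 96.8% | 96.7% | 0.5% |

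**6. Patients without a partner.** If 200 envelopes are used from the shuffled 400, the number on glucagon is hypergeometric (400, 200, 200). The chance of exactly 100 per arm is C(200,100)² / C(400,200) = 0.080. The mean absolute difference between the arms is 8.0 patients. At the 300 patients mentioned as feasible in section 9.1 the figures are 9% and 7. If all 400 cards were used the arms would be equal. Only the 200 case reflects the stated enrolment.

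**The case against.** The strongest reply is that the word is a slip with little consequence. Section 10.4 reasons in terms of two independent groups, and a paired routine needs linked records that section 14.1 would not produce. A biostatistics department is also to be involved, so the error would probably surface at analysis. Under random pairing the two tests have the same type I error and almost the same power. No random pairing changes the verdict at the planned effect, and losing about 8 of 200 patients still leaves far more than the stated 67 per arm.

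Much of this stands. A slip is the likeliest explanation, and it limits the weight of the point. It does not remove it. Naming a department neither defines pairs nor replaces the test that is named, and no other section corrects the sentence. The reassuring error rates also hold only if pairs are formed without regard to outcome, which nothing in the plan secures; step 4 of the working shows how far a result can move otherwise.

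A smaller objection is also fair: section 7.1 does not itself use the term parallel-group. That reading rests on the allocation procedure in section 14.1 and the per-arm sample size in section 10.4, which together leave no other.

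**Conclusion.** The concern holds. As written, section 8.3 prescribes a test that the design cannot supply with pairs, and it does so for every continuous outcome.

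The effect is modest. At the planned 76 s difference the conclusion is safe, and only the width of the interval is arbitrary. The significance verdict is exposed to random re-pairing in a narrow band of observed differences, about 35 to 43 s. About 8 patients would be lost on average at 200 enrolled. Neither an inflated type I error nor a material loss of power is claimed, provided pairing is blind to outcome.

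These sizes assume normal data, a common SD of 140 s, two-sided alpha of 0.05 and, for the interval and verdict figures, 100 patients per arm. The defect itself depends on none of them. It should be fixed, but it does not undermine the trial.

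**What to change.** In section 8.3, replace the matched test with an independent two-sample t-test comparing the randomised arms. For example: continuous outcomes will be compared between the randomised arms with an independent two-sample t-test (Welch), reporting the mean difference and its 95% confidence interval.

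The essential change is from matched to independent groups. An ordinary pooled-variance t-test would cure the defect equally well; Welch and the confidence interval are good-practice additions. If matching really was intended, the plan must instead state the matching variables, how pairs are formed before outcomes are known, and what happens to unpaired patients, and the allocation procedure would have to support it.

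The recommended change costs one sentence. It needs no new data or patients and no change to trial conduct.

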## 8.4 If this study has undergone scientific or scholarly review, please indicate which entity performed the review:

- Cancer Center Protocol Review Committee (PRC) (Full approval is required prior to final CHR approval for cancer-related protocols.)
- CTSI Clinical Research Center (CRC) advisory committee
- Departmental scientific review
- Other:

Specify **Other**:

Department of Gastroenterology Scientific Review

## 9.0 Background

### 9.1 Background:

Colonoscopy is the most commonly performed surgical procedure by gastroenterologists in the United States and is most commonly used for the screening, detection and removal of benign polyps, neoplastic polyps and colon cancer. The National Polyp Study demonstrated a significant decrease in the incidence of colorectal cancer following endoscopic removal of polyps detected during screening colonoscopy. Currently, only 50% of Americans at risk for development of colorectal cancer are being screened with a colonoscopy and attempts to increase the rate of screening will be limited by the total number of colonoscopies that are performed daily in the United States. Thus, identifying interventions that decrease the duration of colonoscopy while maintaining its effectiveness in identifying pre-cancerous polyps can lead to a significant clinical impact.

Colonoscopy is commonly complicated by colonic spasms, particularly in individuals consuming a low residue diet, this leading to patient discomfort, longer procedure times, increased use of sedatives and operator fatigue. Glucagon, an antispasmodic agent, has been demonstrated to reduce intraluminal colonic pressure, colonic wave activity and colonic motility index and is routinely administered prior to colonoscopy by some gastroenterologists. As mentioned above, intravenous glucagon is routinely used during every ERCP examination throughout the United States of America. However, its effect on duration of colonoscopy, adenoma detection rate, patient comfort and operator fatigue has not been definitively answered. There are four previous studies that have evaluated the use of glucagon during colonoscopy and produced conflicting result. Three of these studies were performed prior to 1995 and cannot account for technological improvement leading to improved colonoscope performance. For instance, the first study performed in 1978 took an average of 50 minutes to perform a colonoscopy, almost twice as long as a colonoscopy performed today. Furthermore, each study was limited by small sample sizes (~30 subjects in each study group) and produced conflicting results. One of the studies demonstrated that glucagon decreases total colonoscopy time while the other two studies demonstrated no effect. A recent randomized control trial demonstrated improved cecum insertion time, lower patient pain score and easier scope manipulation with glucagon supplementation but failed to produce a significant clinical impact due to a small sample size (30 subjects in each study group).

We propose to definitively demonstrate the positive effect of glucagon during colonoscopy by performing a placebo-controlled randomized clinical trial involving a large sample size. We aim to evaluate cecum intubation time, total procedure time, adenoma detection rate, degree of spasm, adequacy of visualization, and patient pain score. We will also determine blood glucose level at the end of the procedure to determine the effect of glucagon therapy during colonoscopy. The primary endoscopist for this study, [name], performs or supervises ~15 colonoscopies per week therefore we can expect to enroll at least 300 outpatient subjects over a one-year period.

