### 10.6 Inclusion criteria:

Any subject who has already been already cleared for and scheduled to undergo colonoscopy.

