5. The nursing staff will record, as per standard procedure during colonoscopy, the following: cecum intubation time, colonoscope withdrawal time, total procedure time, use of sedatives for the procedure. The endoscopist will rate the difficulty in scope manipulation, adequacy of visualization and the severity of spasms experienced during the colonoscopy. [name] will review the pathology results and records adenoma detection rate for each subject.

6. The patient will be discharged home according to discharge criteria already established in the outpatient GI endoscopy suite. They will be provided a questionnaire and a pre-addressed envelope prior to discharge.

7. The following day, patients will be asked by mail contact to rate pain, abdominal fullness, and willingness to accept a future colonoscopy if clinically indicated and return their questionnaire in the pre-addressed envelope provided. These will be done according to the enclosed questionnaire sheets.

If you have a procedure table, attach it to the submission with your other study documents.

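### No baseline variable is prespecified for recording or adjustment, although the protocol names low-residue diet as a driver of spasm and long procedures; the cost is some precision and a planned check of balance, not bias

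*Combined protocol and SAP*

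**What the plan says.** Section 9.1 names one prognostic factor: "Colonoscopy is commonly complicated by colonic spasms, particularly in individuals consuming a low residue diet". The same sentence says that spasm leads to patient discomfort, longer procedures, more sedative use and operator fatigue. Several of these are outcomes in Section 8.2 (procedure times, sedatives, spasm, pain).

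Section 14.1 then sets out the procedures. Step 2 covers chart screening, consent and numbering, and steps 3 and 4 cover drug preparation and dosing. In step 5 the nurses record "cecum intubation time, colonoscope withdrawal time, total procedure time, use of sedatives for the procedure", the endoscopist gives ratings, and adenoma findings come from pathology. Step 7 collects next-day patient ratings. Every item named is measured during or after the procedure.

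Entry is broad: "Any subject who has already been already cleared for and scheduled to undergo colonoscopy", subject to the exclusions in Section 10.7. Allocation is by shuffled cards with no stratification. On analysis, Section 8.3 says "Matched student t-test will be used for continuous variables", with a chi-square test for categorical variables. It names no covariate. The word 'matched' comes with no matching variable or pairing, so it supplies no adjustment.

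**The concern.** The protocol identifies a patient characteristic that it believes drives the outcomes, and then neither records it, stratifies on it nor adjusts for it. Variation due to that characteristic therefore stays in the error term of cecal intubation time and the other continuous outcomes. A table comparing the arms at entry is not planned either, and a trial meant to settle conflicting earlier results needs one.

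The timing matters for diet in particular. Age, sex and indication can be read from charts that Sections 14.1 and 21.2 already have opened for screening. Recent diet may not be in the chart, and once the procedure is over it may no longer be obtainable reliably. The choice of covariates also needs to be fixed before the data are seen; otherwise later adjustment is open to the charge of selection.

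**Working it through.** **Inputs.** Section 10.4 reports that "the mean cecum intubation time was 294 seconds in the glucagon group and 370 seconds in the placebo group". The SD given there is 140 s. The difference is 370 − 294 = 76 s. Sections 10.1 and 10.2 give 200 patients, so about 100 per arm. The share of variance explained by baseline covariates (R²) is not in the documents; a range of 0.02 to 0.30 is assumed.

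**The plan's own figure.** Section 10.4 sets 90% power and a 5% significance level and arrives at 67 per arm. Two-sided testing is assumed, since sidedness is not stated.

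- n per arm = 2 × (1.960 + 1.282)² × 140² / 76² = 71.3, so 72 (73 with the t distribution). The stated 67 is not reproduced.
- At 67 per arm the SE is 140 × √(2/67) = 24.2 s and power is Φ(76/24.2 − 1.96) = 0.88.

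That discrepancy is a separate matter. Planned enrolment exceeds both figures, so 100 per arm is used below.

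**Unadjusted precision at 100 per arm.**

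- SE = 140 × √(2/100) = 19.8 s
- 95% half-width = 1.96 × 19.8 = 38.8 s
- Power = Φ(76/19.8 − 1.96) = 0.970

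**With adjustment.** In a linear model the residual SD becomes 140 × √(1 − R²).

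| Assumed R² | Residual SD (s) | 95% half-width (s) | Power, 100 per arm |
|---|---|---|---|
| 0 | 140.0 | 38.8 | 0.970 |
| 0.02 | 138.6 | 38.4 | 0.972 |
| 0.05 | 136.5 | 37.8 | 0.976 |
| 0.10 | 132.8 | 36.8 | 0.982 |
| 0.20 | 125.2 | 34.7 | 0.990 |
| 0.30 | 117.1 | 32.5 | 0.996 |

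The interval narrows by 1 − √0.98 = 1% at the bottom of the range and 1 − √0.70 = 16% at the top. The formula ignores the cost of estimating the covariate coefficients. This is roughly one part in 200 of the variance for each, so four coefficients cost about 4/200 = 2%. At R² = 0.02 the net gain is then close to nil.

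**Diet alone.** For a yes/no factor with prevalence p and a difference D in mean time, R² = p(1 − p)D²/140². Neither p nor D is in the documents. Taking D = 76 s for illustration, p = 0.1 gives 0.09 × 5776/19600 = 0.03 and p = 0.5 gives 0.25 × 5776/19600 = 0.07. Diet by itself would therefore probably sit towards the lower end of the table.

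**Arm-by-diet interaction.** With 200 patients and SD 140 s, the SE of the interaction is 140 × √(4/50) = 39.6 s if half the patients are on the diet. It is 140 × √(2/20 + 2/80) = 49.5 s if 20% are. The interaction detectable with 80% power is about 2.8 times the SE, or 111 to 139 s. That is larger than the whole expected treatment effect of 76 s.

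**The case against.** The strongest reply is that an unadjusted comparison in a randomised trial is valid and unbiased, that power is already about 97% at the planned size, and that formal analysis is left to a biostatistics department (Section 8.3). All of this stands, and it keeps the point modest.

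It can also be said that Section 14.1 is not a complete list. End-of-procedure glucose is planned in Sections 9.1 and 16.5 but does not appear there. Section 18.1 says in general terms that chart information will be obtained, and the questionnaires attached under Section 14.2 are not in the text available. So the supportable statement is that no baseline variable is prespecified, not that none will ever be recorded.

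Three stronger readings are tempting, and the documents do not support them:

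- A reader might infer that an imbalance between arms could be neither seen nor corrected. Age, sex and indication could be abstracted from charts later; only diet is at real risk of being lost.
- A reader might carry the precision gain over to adenoma detection. The √(1 − R²) formula belongs to a linear model. If detection is analysed as a binary outcome, an adjusted logistic model estimates a different odds ratio and does not shrink its standard error in this way.
- A reader might think that diet would show whether glucagon works best in spasm-prone patients. The interaction is too imprecise for that, and spasm is already graded as an outcome.

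Finally, only diet is linked to the outcomes by the documents. They do not show that age, sex or indication is prognostic.

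**Conclusion.** The point holds as a gap in prespecification with a modest cost. The plan names no baseline variable to record or adjust for, while its own background identifies low-residue diet as a driver of the outcomes. The treatment comparison is not biased by this. What is lost is a planned description of the arms and some precision: a half-width of 38.8 s against 38.4 to 32.5 s for an assumed R² of 0.02 to 0.30. Power moves from 0.970 to between 0.972 and 0.996.

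These figures rest on the protocol's SD of 140 s, 100 patients per arm, two-sided 5% testing and an R² that the documents do not supply. The gain would matter more if the trial stopped at 67 per arm. There power is 0.88, and 90% would need a residual SD of 135.7 s, that is R² = 1 − (135.7/140)² = 0.06. The change is worth making because it is cheap and because diet may be unrecoverable afterwards, not because the trial fails without it.

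**What to change.** - **Section 14.1, step 2.** Before the study number is assigned, record age, sex and colonoscopy indication from the chart already reviewed. Add one coordinator question on recent low-residue diet, with the diet and the recall period defined in advance. Recording before numbering keeps the data independent of allocation.
- **Section 8.3.** Replace the t-test for cecal intubation time and the other continuous outcomes with linear regression on arm plus these prespecified covariates. Report the unadjusted comparison alongside, and a baseline table by arm.
- **Limits to state.** Claim no matching precision gain for adenoma detection. Omit the arm-by-diet interaction or report it as descriptive only.

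The cost is a few lines of data entry per patient, one extra question in a conversation that already takes place, and a short rewording of Section 8.3. No extra patients or visits are needed.

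### Operator is left out of both the randomisation and the analysis, so any between-operator variance stays in the error: a modest, cheaply recovered loss of precision, not a bias

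*Combined protocol and SAP*

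**What the plan says.** - **Who does the procedures.** Section 9.1, estimating recruitment, says that the primary endoscopist "performs or supervises ~15 colonoscopies per week". The number and grade of the supervised operators are not given.
- **Allocation.** Section 14.1, step 1: "We will create 400 cards with either glucagon or placebo written on them in a 1:1 distribution". The cards form a single shuffled series with no strata.
- **Analysis.** Section 8.3: "Matched student t-test will be used for continuous variables and the Chi-square test will be used for categorical variables". It names no covariate, operator term or matching factor. It adds that "The UCSF Department of Epidemiology and Biostatistics will be involved in the formal statistical analysis", but gives no model.
- **Outcomes.** In 14.1, step 5, nurses record "cecum intubation time, colonoscope withdrawal time, total procedure time, use of sedatives for the procedure". The same step says: "The endoscopist will rate the difficulty in scope manipulation, adequacy of visualization and the severity of spasms experienced during the colonoscopy". Section 14.2 puts these ratings on a 100 mm visual analog scale. Operator identity is not among the items listed, and the text does not say whether the rater is the person holding the scope or the supervisor.
- **Sample size.** Section 10.4 reports from an earlier trial that "the mean cecum intubation time was 294 seconds in the glucagon group and 370 seconds in the placebo group", with an SD of 140 s, and derives 67 per arm. Section 10.1 plans 200 subjects.

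**The concern.** Insertion and withdrawal times plausibly depend on who holds the scope. Three of the aims in 8.2 (visualization, manipulation, spasm) are subjective scores, which would also carry rater differences if each operator scores their own cases. A comparison that ignores operator puts that variation into the residual and widens the interval for the glucagon effect. With no stratification, the arms can also differ by chance in their share of supervised cases, and the stated tests do not correct for it. The word matched in 8.3 gives no protection, because patients are randomised individually and no pairs are defined.

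At stake is efficiency. The ratings have no power calculation at all, so precision there rests on whatever the enrolled number happens to give.

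**Working it through.** **Inputs from the documents.** Difference 370 − 294 = 76 s; SD 140 s; power 0.90; alpha 0.05, sidedness not stated (all 10.4). Enrolment 200 (10.1), so about 100 per arm at 1:1.

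**Assumed, because the documents are silent.** The share ρ of variance lying between operators, taken as 0 to 0.30, and no dropout.

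**1. The plan's own figure.** n per arm = 2(1.960 + 1.282)² × 140² / 76² = 71.3, so 72 two-sided (73 by the exact t-test). One-sided it is 59. The stated 67 is not reproduced; it has two-sided power 0.881 (t-test 0.877). That discrepancy is a separate matter, and both 67 and 100 per arm are carried below.

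**2. If 140 s is the total SD.** Adjusting for operator leaves a residual SD of 140√(1 − ρ). Power = Φ(76 / (SD√(2/n)) − 1.960). With ρ = 0 and n = 100: 140√(2/100) = 19.80; 76/19.80 = 3.839; Φ(1.879) = 0.970.

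| ρ (assumed) | Residual SD, s | n per arm for 0.90 | Power at 67 per arm | Power at 100 per arm |
|---|---|---|---|---|
| 0 (same as unadjusted) | 140.0 | 72 | 0.881 | 0.970 |
| 0.05 | 136.5 | 68 | 0.897 | 0.976 |
| 0.10 | 132.8 | 65 | 0.912 | 0.982 |
| 0.20 | 125.2 | 58 | 0.940 | 0.990 |
| 0.30 | 117.1 | 50 | 0.964 | 0.996 |

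Exact t-test values at ρ = 0.30 are 0.961 (67 per arm) and 0.995 (100 per arm). The standard error shrinks by the factor √(1 − ρ): 0.949 at ρ = 0.10 and 0.837 at ρ = 0.30, so by 5% and 16%.

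**3. If 140 s is within-operator only.** Section 10.4 does not say which it is. The unadjusted test would then face a total SD of 140/√(1 − ρ): 147.6, 156.5 and 167.3 s at ρ = 0.10, 0.20 and 0.30. Its power would be 0.954, 0.930 and 0.895 at 100 per arm, and 0.846, 0.802 and 0.748 at 67 per arm. Adjustment would bring these back to about 0.970 and 0.881.

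**4. Validity of the unadjusted test.** Trials were simulated with four operators (assumed), a shuffled deck of 400 and 5,000 runs per setting, taking 140 s as the total SD. Type I error of the unadjusted two-sample t-test at 200 patients was 0.051 at ρ = 0.10 and 0.049 at ρ = 0.30.

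| Patients | ρ | Power, unadjusted | Power, with operator term |
|---|---|---|---|
| 134 | 0.10 | 0.885 | 0.901 |
| 134 | 0.30 | 0.893 | 0.958 |
| 200 | 0.10 | 0.973 | 0.981 |
| 200 | 0.30 | 0.970 | 0.993 |

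**5. Chance imbalance.** If half the cases were supervised (assumed), the between-arm difference in that share at 100 per arm has SD √(2 × 0.5 × 0.5 / 100) = 0.071, about 7 percentage points.

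**The case against.** The case against acting is that little of this is documented. The line in 9.1 is a recruitment estimate, not a description of operators. Section 9.1 speaks of one primary endoscopist, and 14.8 has two named staff present for all potential study cases. If one person rates every case, rater differences vanish. The variance share could be near zero. At the plan's own 76 s and 100 per arm, power is already 0.97. A biostatistics department is to be involved and may choose an adjusted model.

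Most of this stands as a limit on size. It does not remove the point: supervision implies more than one pair of hands, and a department's involvement does not prespecify a model.

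Several stronger readings are tempting, and the documents do not support them:

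- **That operator is already known for every case.** A reader might infer this from the endoscopist's rating form. Step 5 of 14.1 does not list operator identity, and the form is an attachment not included here. The remedy may need a new data field as well as new wording.
- **That operator is always a baseline factor.** Nothing excludes a supervisor taking over part-way. That would happen after the drug is given and could be affected by it, so only the operator assigned beforehand is a safe covariate.
- **That the ratings certainly contain rater variance.** This depends on who rates, which is not stated.
- **That categorical outcomes gain in the same way from logistic regression.** They need not. In an illustrative simulation of 200 patients (two-level operator, log-odds effect 1.2; treatment log-odds effect 0.6; all assumed), adding operator raised the standard error of the treatment log-odds ratio from 0.288 to 0.304 and moved the estimate from 0.56 to 0.61, because the adjusted odds ratio is a different quantity. Power rose only from 0.498 to 0.524.

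**Conclusion.** The point holds as a precision refinement of low severity. Neither the allocation nor the analysis takes account of operator, so whatever between-operator variance exists stays in the error of the procedure times, and of the ratings if the operator gives them.

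A reader might go further and infer a biased comparison or too many false positives. Individual randomisation rules out the first, and the simulated type I error of 0.049 to 0.051 shows no sign of the second.

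For cecal intubation time at the planned enrolment the gain is small if 140 s is the total SD. It is larger if 140 s excludes operator variance or if only 67 per arm are enrolled. For the ratings it cannot be sized. All of these sizes rest on an assumed share of 0 to 30%, since the documents give neither that share nor the number of operators.

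**What to change.** 1. On the endoscopist form, record the operator assigned before the study drug is given, and state who gives the ratings.
2. In 8.3, replace the matched t-test, which has no matching to rest on, with a linear model of each continuous outcome on arm plus the pre-assigned operator category: attending versus supervised, or operator identity if there are few. Report the unadjusted two-sample t-test beside it.
3. Keep the chi-square test for categorical outcomes.

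The cost is a small addition to the form, a short change to 8.3, and one or a few degrees of freedom. If operators prove numerous, the two-level category keeps that cost at one.
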